4.3 Handling of Missing Data

All missing or partially missing data will be presented in the subject data listing as they are recorded on the Case Report Form (CRF) and electronic diary (eDiary).

When appropriate and for a limited number of variables, certain rules described below will be implemented to avoid exclusion of subjects from statistical analyses due to missing or incomplete data.

Bleeding data

For bleeding pattern analyses, missing eDiary will be imputed based on the sponsor’s standard procedures⁽¹¹⁾. Missing bleeding data in the subject diaries will be imputed. For the uterine fibroid daily bleeding diary (UF-DBD), the worst case approach will be used for missing bleeding intensity

for the single or two consecutive missing days (ie, the maximum of the bleeding intensities of the day before and the day after the missing day[s] will be assumed).

After having imputed missing values in the UF-DBD, missing menstrual pictogram (MP) values are imputed in the next step.

For days with bleeding intensity of “mild” or higher in the UF-DBD, missing MP values will be replaced by the mean value of MP values of the days with the same bleeding intensity. In case there are no MP values with the same bleeding intensity, the mean of the MP values of next higher intensity will be used. In case there is no intensity higher than the bleeding intensity of the missing MP values available, no replacement for the missing MP values will be done for such days.

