This definition of bleeding episode, based on the UF-DBD, is the only bleeding definition implemented in the analysis to identify bleeding episodes. The protocol includes a definition of bleeding episode based on the MP, which will be implemented during the screening period to facilitate the assessment of the HMB inclusion criterion (criterion 4, MBL >80 mL) by clinical sites. This latter definition of bleeding period will not be used in the analysis.

Menstrual blood loss for 28 days

Menstrual blood loss for 28 days is defined as the sum of menstrual blood loss [mL] by MP in a 28-day period. Non-overlapping 28-day periods will be created along the different study periods: TPs, break periods (if applicable), and FUP phase. In case of premature discontinuation of study drug the last 28-day period of the respective treatment period might be shorter than 28 days. For details about the volume of MBL assigned to MP, see Appendix 4.

Volume of menstrual blood loss per bleeding episode after the reference end date

Volume of menstrual blood loss for a bleeding episode is the sum of volume of menstrual blood loss [mL] data by MP in the respective episode after the reference end date.

Amenorrhea (defined as < 2 mL during last 28 days of treatment course) assessed by MP method

Amenorrhea is defined as menstrual blood loss less than 2 mL during the last 28 days of the respective treatment period. For missing data replacement please refer to section 4.3.

- i) the sum of the non-missing (i.e. original or imputed) MP values is ≥ 2 mL, or
- ii) there is at least one day with missing MP value and bleeding intensity of “mild” up to “very severe” after having applied the imputation rules, or
- iii) the subject did not complete at least 8 weeks of treatment.

If neither of i), ii) or iii) applies, the subject will be considered as having amenorrhea.

The last days under treatment with 28 days with non-missing (i.e. original or imputed) MP data will be used to calculate whether amenorrhea occurred. Thus, if the last 28 days of treatment include days with missing MP data, the left margin of this interval will be displaced backwards in time and step-wise until the required number of 28 non-missing values are included.

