6.2.3.1 Volume of menstrual blood loss related variables

- Volume of menstrual blood loss per 28 days (assessed by MP)
- Volume of menstrual blood loss per bleeding episode (assessed by MP) for first, second, and third bleeding episode after the end of treatment
- Volume of MBL per bleeding episode within the treatment break. All days of the bleeding episodes will be used even if some days of the episode lie outside the treatment break. The first, second and third bleeding episode will be considered. This endpoint is only applicable for VPR groups.
- Amenorrhea (yes/no), defined as menstrual blood loss <2 mL during last 28 days of treatment, based on the MP

- Absence of bleeding (spotting allowed) during the last 28 days of the treatment; based on the UF-DBD

Analysis for volume of menstrual blood loss per 28 days will be done by treatment group and Time interval D (according to [Figure 4-1](#)). Amenorrhea and absence of bleeding will be analyzed by treatment group and TP. For treatment group B, volume of menstrual blood loss per bleeding episode (assessed by MP) for first, second, and third bleeding episode after the end of treatment will only be done after the reference end date. Volume of MBL per bleeding episode within the treatment break for treatment group B will not be analyzed.

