6.5.3.13 UF-DBD bleeding pattern per 28 days and 84 days based on UF-DBD

The bleeding data recorded on the UF-DBD will be summarized using descriptive statistics in the safety analysis set by treatment groups using time intervals C and time intervals D. A reference period of 28 days will be used for most analyses, which corresponds with the time interval D. When a reference period of 84 days is used the time intervals D will be modified accordingly.

The bleeding intensity will be summarized by bleeding category using frequency tables by reference period of 28 days and 84 days.

The maximum bleeding intensity will be summarized using frequency tables by 28 days reference period.

The number of bleeding days will be analyzed by 28 days reference period and with the following bleeding categories:

- non-bleeding,
- spotting-only,
- bleeding (category of bleeding intensity \geq mild)
- bleeding including spotting (category of bleeding intensity \geq spotting)
- mild
- moderate
- severe
- very severe

For the safety bleeding analysis, and in contrast with the analysis of efficacy variables based on bleeding data, bleeding induced by endometrial biopsies will not be excluded.

An incomplete period which does not comprise 28 (or 84, respectively) days will be analyzed for any of the considered time periods of Intervals C. The analysis of this incomplete period is based on all subjects for whom the length of the considered time period is not a multiple of 28 (or 84, respectively) days. Subject's data from the last $x < 28$ ($x < 84$) days of the considered time period will be included.

7. Subgroup analyses

Subgroups for endpoints as described in section 6.2.2 and 6.2.3.1

- 1) Subjects who fulfill the inclusion criteria of HMB > 80.00 mL by MP during screening period (depicted by Baseline Volume of menstrual blood loss per 28 days) and at least one fibroid > 3 cm at baseline by Ultrasound vs. subjects who did not fulfill these criteria at baseline.

8. Document history and changes in the planned statistical analysis

SAP version 1.0. dated 31 Jul 2017

9. References

1. Recording and Evaluation of Bleeding Data Version 6.0 (BHC-RD-OI-107)
2. Nikica Živković¹, Krešimir Živković², et al. Measuring the volume of uterine fibroids using 2- and 3- dimensional ultrasound and comparison with histopathology. Acta Clin Croat. 2012; 51:579-589

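### Menstrual blood loss per 28 days is an unscaled sum that is tabulated together with blocks shorter than 28 days, so columns labelled as 28-day periods mix full sums with fragments

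*SAP*

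**What the plan says.** Section 4.5 gives the definition: "Menstrual blood loss for 28 days is defined as the sum of menstrual blood loss [mL] by MP in a 28-day period". The blocks do not overlap and run through treatment periods (TPs), breaks and follow-up. The same paragraph adds: "In case of premature discontinuation of study drug the last 28-day period of the respective treatment period might be shorter than 28 days". It gives no scaling, no minimum number of days and no separate category for a short block.

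Section 6.2.3.1 sets the presentation: "Analysis for volume of menstrual blood loss per 28 days will be done by treatment group and Time interval D". Interval D in Figure 4-1 is the grid of 28-day slices of each TP, break and follow-up phase.

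Three other rules bear on where short blocks arise, all in section 4.5. The length of a break depends on one or two bleeding episodes, and the break ends the day before the next TP. Group B has no breaks, and its TPs are consecutive 84-day intervals from randomization. The last TP in every group ends at the reference end date, which for group B is the EoT visit.

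On missing MP values, section 4.3 imputes from days of the same or the next higher bleeding intensity. Where no such value exists, "no replacement for the missing MP values will be done for such days".

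**The concern.** A column such as the second slice of the first break (days 29-56) should describe blood loss over 28 days. As the plan is written, it averages subjects with a full 28-day sum and subjects whose slice lasted only a few days. The mean and median of such a column have no clear meaning, and changes across columns can reflect block length rather than blood loss.

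The SAP deals with the same problem for three related variables but not for this one:

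- The number of bleeding days is normalized to 28 and 365 days (section 4.5).
- The amenorrhea window is moved back until it holds 28 non-missing days (section 4.5).
- The safety bleeding analysis treats incomplete periods apart: "The analysis of this incomplete period is based on all subjects for whom the length of the considered time period is not a multiple of" the reference length (section 6.5.3.13).

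There is a smaller gap next to it. For amenorrhea, a subject is a non-responder if "there is at least one day with missing MP value and bleeding intensity of" mild or higher. The volume variable has no matching rule, so two programmers could handle the same day differently.

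**Working it through.** The SAP states no figure for this variable, so there is none to reproduce. The check has four steps.

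**1. Where short blocks arise.**
- *Discontinued TP:* the SAP says so itself.
- *Break (vilaprisan groups only):* the last slice is full only if the break length is a multiple of 28. A 36-day break, for example, gives 28 + 8 days.
- *Group B:* a complete TP gives 84 / 28 = 3 full blocks. The last TP is cut at the EoT visit, so its last block can be short.
- *Follow-up:* it ends at the last visit, so its last slice can be short in any group.

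A vilaprisan subject can thus meet a short block at the end of each break, while a group B subject has no breaks. The number of opportunities differs by design. The SAP gives no counts.

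**2. What a short block captures.** Assumptions, not from the SAP: one 7-day bleed per 28 days, equal volume on each bleeding day. A block has L days; R is the raw sum as a share of the true 28-day volume. With the bleed at a random phase, the mean of R is L/28. The last two columns place the bleed at fixed positions.

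| L (days) | Mean R = L/28 | R, bleed at start of block | R, bleed on days 22-28 |
|---|---|---|---|
| 7 | 25% | 100% | 0% |
| 14 | 50% | 100% | 0% |
| 21 | 75% | 100% | 0% |

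On average the raw sum falls short, but an individual short block can hold the whole bleed or none of it.

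**3. Effect on a column mean.** Let a share f of blocks be short, with length spread evenly over 1 to 27 days (mean 14) and random phase. The mean is then understated by f × (1 − 14/28) = f × 50%.

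| f (assumed) | Understatement |
|---|---|
| 5% | 2.5% |
| 10% | 5% |
| 20% | 10% |
| 30% | 15% |

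The loss in mL depends on the level of bleeding. At L = 14, an assumed true loss of 150 mL loses 75 mL on average; an assumed 2 mL loses 1 mL.

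**4. Would scaling by 28/L repair it?** At random phase the scaled sum averages 100% of the true volume. However, its SD is 130%, 82% and 43% of that volume for L = 7, 14 and 21. With the bleed at the start of the block it gives 28/L, that is 400%, 200% and 133%. Scaling replaces one distortion with another.

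**Missing MP days.** If such days were counted as zero, 1, 2 or 3 of 7 equal bleeding days would leave 6/7 = 86%, 5/7 = 71% or 4/7 = 57% of the volume. The SAP does not say that they are counted so.

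**The case against.** The strongest reply is that the practical harm is small. This is one of several other efficacy variables, analyzed descriptively. The primary variable is bone mineral density, and the secondary efficacy variable, number of bleeding days, is normalized. Section 6.2.3.1 also reports volume per bleeding episode within the break, using all days of the episode even if some lie outside it, and volume per episode after the end of treatment. Those variables are not cut by blocks and partly cover break blood loss. All of this stands and limits the weight of the point.

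Four stronger readings are tempting, and the SAP does not support them.

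- *The rule favours vilaprisan.* Break columns have no group B counterpart. Group B's last block can be cut too. Under Amendment 9 (section 3), vilaprisan subjects were to finish their current 3-month block. If loss on treatment is low (an assumption), truncation removes few mL there and more in group B. Blocks are contiguous, so bleeding cut off when a TP starts is counted in that TP's first block and raises the on-treatment figure.
- *Unimputed MP days count as 0 mL.* Section 4.3 says only that they are not replaced. The sum could equally become missing. The defect is silence.
- *A break fragment is understated by a fixed percentage.* Break length is tied to bleeding episodes, so the random-phase average does not describe the tail of a break.
- *TPs longer than 84 days create further fragments.* Section 4.5 says only that the TP is then longer, and Figure 4-1 shows TP slices up to days 57-84. Where the extra days go is not stated.

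**Conclusion.** The point holds as a defect of definition and presentation. Following the SAP as written, sums over fewer than 28 days enter columns labelled as 28-day periods, with nothing to identify them. Short blocks are structurally more frequent in the vilaprisan groups, because only they have breaks.

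Under random bleed timing, a block of L days captures L/28 of the loss on average, and a column mean falls by half the share of short blocks. That rests on an assumed 7-day bleed, equal daily volume, random phase and evenly spread block lengths. The actual share of short blocks, and the size and direction of any net difference between arms, cannot be determined from the SAP. The change should be made, but no primary or secondary conclusion depends on it.

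**What to change.** In section 6.2.3.1, or in the definition in section 4.5, state that volume of menstrual blood loss per 28 days is summarised for complete 28-day blocks only. Show incomplete blocks in a separate row with their number and length by group, on the model of section 6.5.3.13. Do not use scaling by 28/L as the main analysis; a scaled version could serve as a sensitivity display.

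As a secondary clarification, state how a day of mild or higher intensity whose MP value is still missing after the section 4.3 imputation enters the sum, and report the number of affected blocks by group. Setting every such block to missing has its own cost: it selectively removes blocks with recorded bleeding. That choice is a trade-off to be made openly.

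The cost is a few lines of SAP text and a filter in the programs. Fewer subjects contribute to the last block of each period, and a break shorter than 28 days moves entirely to the incomplete row. For breaks, the per-episode volumes then carry more of the description.

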- The second Analysis TP is assigned the next higher even TP number, starts with day 85 and ends with the last day reported in the original protocol TP, even if this exceeds a total of 168 days.

For example, protocol TP1 = analysis TP1 + analysis TP2. Protocol TP2 = analysis TP 3 + analysis TP 4 etc.

If the original planned protocol TP is less than 85 days, no such second evenly numbered Analysis TP will be assigned. As a result of this a subject in 6/2 regimen might have Analysis TP 1, TP 3 and TP 4, but no Analysis TP 2.

If the end date of the current treatment period is equal to the start date of the next treatment period based on CRF entries, it is assumed that the current treatment period ended one day earlier. The end date of the current treatment period is therefore moved back by one day.

For all TPs excluding the last TP, in case end of TP date is still missing, it will be replaced by the date of the last study drug intake within the respective TP according to diary (EXCATN=5 and EXMEDN>=1).

Subjects in treatment group B don't have any breaks. In the treatment group B TPs will be defined as consecutive 84-day time intervals starting with the date of randomization.

Replacement rules for missing end date of the last TP are analogue to those described for reference end dates.

TPs will be numbered sequentially.

Time intervals

Due to the complex visit schedule of the studies, a time-interval based approach is chosen to present data over time. Therefore, time intervals are defined which are used for different analysis topics.

The selection of time intervals used for a certain analysis topic will be described within each section.

An overview of the time intervals is given in [Figure 4-1](#).

Figure 4-1: Time interval overview

BL/Post baseline	Post baseline																										
Intervals A	Treatment Phase																		FUP Phase								
Intervals B	TP1 + BR1						TP2 + BR2						TPx						FUP1+2			FUP ...					
Intervals C	TP1			BR1			TP2			BR2			TPx			FUP1			FUP2			FUP ...					
Intervals D	BL	BL	BL	TP1	TP1	TP1	BR1	BR1	BR1	TP2	TP2	TP2	BR2	BR2	BR2	TPx	TPx	TPx	FUP	FUP	FUP	FUP	FUP	FUP	FUP	FUP	FUP
	1-28	29-56	57-x	1-28	29-56	57-84	1-28	29-56	...	1-28	29-56	57-84	1-28	29-56	...	1-28	29-56	57-84	1-28	29-56	57-84
AE Intervals	Pre-treatment			"on" (TP1 + 8d)			"off"			"on" (TP2 + 8d)			"off"			"on": TPx + 8d			"off"			Post-treatment (Start: day 61 after EoT)					

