The left margin may be displaced backwards at maximum up to the end of the first bleeding episode when treatment was started in respective treatment period. For TP with an even number in the 6/2 regiment, the left margin may be displaced backwards at maximum up to the end of the first bleeding episode of the preceding odd-numbered TP from the same protocol defined 168-day TP when treatment was started.

Absence of bleeding (spotting allowed) during the last 28 days of the treatment; based on the UF-DBD

Absence of bleeding is defined as no bleeding (spotting allowed) during the last 28 days of the respective treatment period based on the UF-DBD. For missing data replacement please refer to section 4.3.

The last days under treatment with 28 days with non-missing bleeding eDiary data will be used to calculate whether absence of bleeding occurred. Thus, if the last 28 days of treatment include days with missing bleeding eDiary data, the left margin of this interval will be displaced backwards in time and step-wise until the required number of 28 non-missing values are included.

The left margin may be displaced backwards at maximum up to the end of the first bleeding episode when treatment was started in respective treatment period. For TP with an even number in the 6/2 regimen, the left margin may be displaced backwards at maximum up to the end of the first bleeding episode of the preceding odd-numbered TP from the same protocol defined 168-day TP when treatment was started.

Subjects who discontinue treatment prior to completion of 8 weeks of treatment in the respective TP will be considered as not experiencing absence of bleeding.

Number of bleeding days

Number of bleeding days is defined as number of bleeding days (based on the UF-DBD) from Day 1 of the first treatment period until one day before the theoretical next treatment period would start after the last study treatment period. Definition of the day before theoretical next treatment period end date, i.e., theoretical end date for the break period, refers to the rules defined in break period above.

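### The amenorrhea rule gives no outcome when fewer than 28 pictogram values can be found, and its closing default then counts the treatment period as amenorrhea

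*SAP*

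**What the plan says.** The definition is in SAP Section 4.5: "Amenorrhea is defined as menstrual blood loss less than 2 mL during the last 28 days of the respective treatment period". Three conditions follow:

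- i) "the sum of the non-missing (i.e. original or imputed) MP values is ≥ 2 mL, or"
- ii) after imputation, some day still lacks an MP value although the bleeding diary records an intensity of mild or worse for it
- iii) "the subject did not complete at least 8 weeks of treatment"

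The rule closes with "If neither of i), ii) or iii) applies, the subject will be considered as having amenorrhea". The conditions are thus the ways of being classed as not amenorrheic, and amenorrhea is the default.

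The same section asks for 28 non-missing MP values and moves the left margin of the window back to find them. The move is capped: "The left margin may be displaced backwards at maximum up to the end of the first bleeding episode" of the TP. For even-numbered TPs of the 6/2 regimen, the cap is the first episode of the preceding odd TP. No outcome is given if the cap is reached with fewer than 28 values.

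Section 4.3 gives worst-case imputation of the bleeding diary (UF-DBD) "for the single or two consecutive missing days". It imputes MP only on days with an intensity of mild or higher. For group B, "In the treatment group B TPs will be defined as consecutive 84-day time intervals starting with the date of randomization". Section 6.2.3.1 reports amenorrhea by treatment group and TP.

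**The concern.** A default of success is safe only if every route to an unevaluable window is closed first, and here one is open. The 28-value requirement is not tied to any consequence, so the default sentence settles the case.

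The SAP is more careful in comparable places. For time to onset of amenorrhea, Section 4.5 censors women who discontinue a TP when onset cannot be ruled out. Appendix 1 sets a UFS-QoL subscale to missing when half or more of its items are missing. Section 4.1 provides a missing category for frequency tables.

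At stake is the amenorrhea table by arm and TP. In group B, TPs are calendar blocks that exist whether or not a diary was kept, and true amenorrhea should be uncommon. A few default successes could therefore make up much of that arm's reported rate. Two programmers could also derive different tables from the same text.

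**Working it through.** The SAP states no amenorrhea rate, diary-missingness rate or power for this endpoint, so there is no planned figure to reproduce.

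**Step 1: an empty diary against the three conditions.** Take a subject treated for a full 84-day TP with no diary entries in it.

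| Condition | Needs | Empty diary |
|---|---|---|
| i) | recorded or imputed MP summing to 2 mL or more | sum is 0, does not apply |
| ii) | missing MP on a day with known intensity of mild or higher | intensity is missing too, does not apply |
| iii) | less than 8 weeks of treatment | dates come from the eCRF or, in group B, from randomization and the EoT visit (Table 4-1), does not apply |

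None applies, so the default makes her amenorrheic. This takes diary gaps of more than two days to stay missing, which is inferred from Section 4.3.

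**Step 2: where the gap begins and ends.** The rule was run for one fully treated 84-day TP, for every possible last diary day from 0 to 83. Assumptions not in the SAP: first bleed on days 1-5, 20 mL per bleeding day, and 0 mL recorded on bleed-free diary days.

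- *Never suppressed, bleeding 5 days in every 28.* Last diary day 28: days 6-28 give 28 - 5 = 23 values, sum 0 mL, classed as amenorrhea. Last diary day 29: 24 values, sum 20 mL, fails under i). Last diary day 33: 28 values, sum 5 × 20 = 100 mL, fails. She is a success for last diary days 0-28 and a failure from day 29 on.
- *No bleeding after the first episode.* She is a success for every last diary day, but only from day 5 + 28 = 33 does this rest on 28 values.

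In general, 28 values exist once the last diary day reaches the end of the first bleed plus 28: day 3 + 28 = 31 to day 10 + 28 = 38 for bleeds ending on days 3 to 10. For diaries stopping on days 1-6, the run places the cap at day 5. The diary alone could not confirm it, because an episode must be followed by two recorded bleed-free days.

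If 28 values are required, the never-suppressed profile is a success for no last diary day, and the second profile only for days 33-83.

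**Step 3: illustrative size.** Let p be the true rate, assumed equal with and without a full diary, and m the share of subjects in a TP who pass only by default. Both are assumed.

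Reported rate = p(1-m) + m; inflation = m(1-p).

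| m | p = 2% | inflation | p = 70% | inflation |
|---|---|---|---|---|
| 5% | 6.9% | 4.9 | 71.5% | 1.5 |
| 10% | 11.8% | 9.8 | 73.0% | 3.0 |
| 20% | 21.6% | 19.6 | 76.0% | 6.0 |

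At m = 10% in both arms, the difference falls from 70 - 2 = 68 points to 73.0 - 11.8 = 61.2 points. If m is read as everyone with too few diary days, these are upper figures, because some of those women still fail under i), ii) or iii).

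**The case against.** The strongest reply is that the SAP calls 28 values the required number and has a missing category, so subjects short of 28 were meant to be unevaluable. That may be the intent, but the text does not say it, and the explicit default says the opposite.

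Two uncertainties stand. Section 4.3 also refers to a sponsor procedure for bleeding data that is not at hand and might treat longer gaps. And no sentence introduces conditions i)-iii) in the text as read. Their role is inferred from the closing sentence, and a lead-in may have been lost in extraction.

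A reader might infer several stronger points that the SAP does not support:

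- *Any woman who stops her diary but stays in the study for 8 weeks is a success.* With 28 values after the first episode she is judged on her last 28 recorded days, and 2 mL or more fails her. Condition iii) also concerns treatment, not time in the study.
- *The inflation is largest where diary drop-off is largest.* It also depends on 1-p. Group B at m = 10% (p = 2%) gains 9.8 points, while vilaprisan at m = 20% (p = 70%) gains only 6.0.
- *The error favours vilaprisan.* At equal m it narrows the difference. The direction in practice depends on where the gaps fall.
- *Absence of bleeding has the same defect.* That rule has no default-success sentence; its outcome below 28 values is simply unstated.

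**Conclusion.** The concern holds in a limited form. For a subject with at least 8 weeks of treatment and fewer than 28 MP values after maximum displacement, the literal rule returns amenorrhea unless condition i) or ii) applies. This is a wrong classification, not only a missing detail, and it reaches the extreme of a TP with no bleeding data at all.

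Its size in this trial cannot be computed. Under the stated assumptions it is m(1-p), so at a given m it is larger where true amenorrhea is rare, as expected in group B. The conclusion rests on the default sentence being complete as read and on longer diary gaps staying missing.

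Severity is moderate. Amenorrhea is one of the other efficacy variables in Section 6.2.3.1 and is analysed descriptively. The primary safety variable (lumbar-spine BMD) and the secondary efficacy variable (number of bleeding days) do not use this rule.

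**What to change.** Add to the amenorrhea rule in Section 4.5:

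- If fewer than 28 evaluable days remain after the maximum displacement of the left margin and none of i)-iii) applies, class the subject-TP as missing, using the category in Section 4.1.
- Provide a sensitivity table that counts these subject-TPs as not amenorrheic.
- Count a day with a UF-DBD entry of no bleeding and a blank MP as an evaluable 0 mL day. The SAP does not say that 0 mL is recorded on such days. If it is not, a plain count of MP values would remove women who are truly amenorrheic.

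For absence of bleeding, state the same outcome below 28 evaluable days, for consistency.

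The cost is one sentence and one derivation line per rule, plus one sensitivity table. The main table will have a somewhat smaller denominator, and the sensitivity table somewhat lower amenorrhea rates.
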